## 8.0 DRUG INFORMATION

### 8.1 Durvalumab

#### 8.1.1 Other names

MEDI4736

#### 8.1.2 Classification - type of agent

Durvalumab is a human IgG1k mAb.

#### 8.1.3 Mode of action

Durvalumab, a human IgG1k mAb directed against PD-L1, and with reduced binding to C1q and the FcY receptors

#### 8.1.4 Storage and stability

All investigational products should be kept in a secure and dry place. Vials should be stored at 2°C to 8°C (refrigerated) and not be frozen.

#### 8.1.5 Protocol dose specifics

Doses of 1500mg for patients (>30 kg) will be administered using an intravenous (IV) bag containing 0.9% (weight/volume) saline or 5% (w/v) dextrose, with a final durvalumab (MEDI4736) concentration ranging from 1 to 20 mg/mL and delivered through an IV administration set with a 0.2- or 0.22-µm in-line filter.

If a patient's weight falls to 30kg or below the patient should receive weight-based dosing equivalent to 20 mg/kg of durvalumab Q4W until the weight improves to >30 kg, at which point the patient should start receiving the fixed dosing of durvalumab 1500mg Q4W. The appendix includes an example of a weight-based dose calculation. (Appendix C).

For 1500mg durvalumab dose (patients > 30kg), add 30.0 mL of durvalumab (MEDI4736) (ie, 1500mg of durvalumab [MEDI4736]) to the IV bag. The IV bag size should be selected such that the final concentration is within 1 to 20 mg/mL, and the bag is mixed by gentle inversion to ensure homogeneity of the dose in the bag.

For the 750mg durvalumab maintenance dose, add 15.0 mL of durvalumab (MEDI4736) (ie, 750mg of durvalumab [MEDI4736]) to the IV bag. The IV bag size should be selected such that the final concentration is within 1 to 20 mg/mL, and the bag is mixed by gentle inversion to ensure homogeneity of the dose in the bag. Weight based dosing is not required for the 750mg durvalumab dose.

Patients will be treated with durvalumab 1500mg intravenously (IV) every 4 weeks for a total of 4 doses (along with tremelimumab 75mg IV every 4 weeks for a total of 4 doses). After completion of the 4 doses of combination therapy, durvalumab will be continued at a dose of 750mg every 2 weeks for up to 18 additional doses.

#### **8.1.6 Preparation**

The Investigational Products Supply section of AstraZeneca/MedImmune will supply durvalumab to the investigator as a 500-mg vial solution for infusion after dilution. The solution contains 50 mg/mL durvalumab, 26 mM histidine/histidine-hydrochloride, 275 mM trehalose dihydrate, and 0.02% (weight/volume) polysorbate 80; it has a pH of 6.0. The nominal fill volume is 10.0 mL.

The dose of durvalumab (MEDI4736) for administration must be prepared by the Investigator's or site's designated IP manager using aseptic technique. Total in-use storage time from needle puncture of durvalumab vial to the start of administration should not exceed 4 hours at room temperature or 24 hours at 2°C to 8°C (36°F to 46°F). If in-use storage time exceeds these limits, a new dose must be prepared from new vials. Infusion solutions must be allowed to equilibrate to room temperature prior to commencement of administration.

#### **8.1.7 Route of administration for this study**

The liquid product is to be diluted with 0.9% (w/v) saline or 5% (w/v) dextrose for IV infusion.

#### **8.1.8 Incompatibilities**

No formal drug-drug interaction studies have been conducted with durvalumab. There are no known clinically significant interactions of durvalumab with other medicinal products.

#### **8.1.9 Availability & Supply**

Durvalumab will be supplied by AstraZeneca as a 500-mg vial concentrate solution for infusion. Investigational products will be supplied by MedImmune in containers with identical appearances in coded kits for each product respectively. Each investigational product kit has a unique number that is printed on all labels within the kit (ie, the outer carton label and the label of each container within the carton). Each carton and vial is labeled with the same unique sequence number range. MEDI4736 will be supplied in liquid form.

Durvalumab will be provided to Northwestern University by MedImmune, Northwestern University will request durvalumab submitted via email indicating the amount of bottles required to the contact below:

[name]  
Sr. Clinical Project Manager  
[contact]  
P: [contact]| F: [contact]

Please allow approximately 10 days for drug delivery.

#### **8.1.11 Nursing implications**

Durvalumab will be administered as an IV infusion over approximately 1 hour in duration ( $\pm$  5 minutes). If the infusion is less than 55 minutes or more than 65 it is considered a deviation. The IV line will be flushed with a volume of IV diluent equal to the priming volume of the infusion set used after the contents of the IV bag are fully administered, or complete the infusion according to institutional policy to ensure the full dose is administered and document if the line was not flushed.

Durvalumab infusion will start approximately 1 hour after the end of tremelimumab infusion. The duration will be approximately 1 hour ( $\pm$  5 minutes) for each infusion. Refer to Section 4.2.1 for monitoring of vitals.

Since the compatibility of durvalumab with other IV medications and solutions, other than normal saline (0.9% [w/v] sodium chloride for injection) and 5% (w/v) dextrose, is not known, the durvalumab solution should not be infused through an IV line in which other solutions or medications are being administered. No incompatibilities between durvalumab and polyvinylchloride or polyolefin IV bags have been observed. The date, start time, interruption, and completion time of

durvalumab administration must be recorded in the source documents.

In the event that there are interruptions during infusion, the total allowed time should not exceed 8 hours at room temperature. If either preparation time or infusion time exceeds the time limits a new dose must be prepared from new vials. Durvalumab (MEDI4736) does not contain preservatives, and any unused portion must be discarded.

#### **8.1.12 Return and Retention of Study Drug**

All unused investigational products will be returned to a MedImmune-authorized depot or disposed of upon authorization by MedImmune according to the investigational site policy.

### **8.2 Tremelimumab**

#### **8.2.1 Other names**

n/a

#### **8.2.2 Classification - type of agent**

Tremelimumab is being developed as an immunotherapeutic agent for various cancers.

#### **8.2.3 Mode of action**

Tremelimumab is a human IgG2 anti-CTLA-4 mAb.

#### **8.2.4 Storage and stability**

Investigational product must be stored at 2 to 8 degrees Celsius and must not be frozen.

#### **8.2.5 Protocol dose specifics**

Tremelimumab 75mg IV every 4 weeks for a total of 4 doses for patients > 30kg.

A dose of 75 mg (for patients >30kg in weight) will be administered using an IV bag containing 0.9% (w/v) saline or 5% (w/v) dextrose, with a final tremelimumab concentration ranging from 0.10 to 10 mg/mL, and delivered through an IV administration set with a 0.2- or 0.22- $\mu$ m in-line filter. Add 3.8 mL (ie, 75 mg of tremelimumab, with the dose volume rounded to the nearest tenth mL) to the IV bag. The IV bag size should be selected such that the final concentration is within 0.10 to 10 mg/mL. Mix the bag by gently inverting to ensure homogeneity of the dose in the bag.

If a patient's weight falls to 30kg or below the patient should receive weight-based dosing equivalent to 1mg/kg tremelimumab Q4W until the weight improves to >30 kg, at which point the patient should start receiving the fixed dosing of tremelimumab 75 mg Q4W. The appendix includes an example of a weight-based dose calculation. (Appendix D)

#### **8.2.6 Preparation**

The dose of 75 mg of tremelimumab for administration must be prepared by the Investigator's or site's designated IP manager using aseptic technique. Total in-use storage time from needle puncture of tremelimumab vial to start of administration should not exceed 4 hours at room temperature or 24 hours at 2°C-8°C (36°F-46°F). If storage time exceeds these limits, a new dose must be prepared from new vials. The infusion solution in the prepared final IV bag should be equilibrated to room temperature prior to administration. Tremelimumab does not contain preservatives and any unused portion must be discarded.

#### **8.2.7 Route of administration for this study**

IV

#### **8.2.8 Incompatibilities**

No formal drug-drug interaction studies have been conducted with tremelimumab. However, in RCC studies, acute renal failure has been reported with the combination of tremelimumab and sunitinib. It is unknown whether a similar reaction will be observed when tremelimumab is combined with other tyrosine kinase inhibitors.

#### **8.2.9 Availability & Supply**

Tremelimumab will be supplied by AstraZeneca either as a 400-mg or a 25-mg vial solution for infusion after dilution. The solution contains 20 mg/mL tremelimumab, 20 mM histidine/histidine hydrochloride, 222 mM trehalose dihydrate, 0.27 mM disodium edetate dihydrate, and 0.02% weight/volume (w/v) polysorbate 80; it has a pH of 5.5 and density of 1.034 g/mL. The nominal fill volume is 20.0 mL for the 400-mg vial and 1.25 mL for the 25-mg vial. Investigational product vials are stored at 2°C to 8°C (36°F to 46°F) and must not be frozen. Drug product should be kept in original container until use to prevent prolonged light exposure.

Tremelimumab will be provided to Northwestern University by MedImmune.. Northwestern University will request tremelimumab submitted via email indicating the amount of bottles required to the contact below:

[name]  
Sr. Clinical Project Manager  
[[contact]](mailto:[contact])  
P: [contact] F: [contact]

Please allow approximately 10 days for drug delivery.

#### **8.2.11 Nursing implications**

The first day of dosing is considered Day 1. Infusion duration for tremelimumab will be approximately 1 hour ( $\pm$  5 minutes). If the infusion is less than 55 minutes or more than 65 it is considered a deviation. Tremelimumab will be administered first; followed by Durvalumab approximately 1 hour after the end of the tremelimumab infusion.

Each dose of investigational product should be administered using the following guidelines:

1. Investigational product must be administered at room temperature by controlled infusion into a peripheral vein or central line. Prior to the start of the infusion, ensure that the bag contents are at room temperature to avoid an infusion-related reaction due to the administration of the solution at low temperatures.
2. A physician must be present at the site or immediately available to respond to emergencies during all administrations of investigational product. Fully functional resuscitation facilities should be available. Investigational product must not be administered via IV push or bolus but as a slow IV infusion. The entire content of each IV bag will be infused using an infusion pump.
3. The infusion lines should be attached only at time of use. Lines used for infusion during dose administration will need to be equipped with 0.22- or 0.2- $\mu$ m in-line filters.
4. The duration of the investigational product administration will be recorded.

Tremelimumab will be administered as an IV infusion over approximately 1 hour ( $\pm$  5 minutes). The IV line will be flushed with a volume of IV diluent equal to the priming volume of the infusion set used after the contents of the IV bag are fully administered (unless prohibited by institutional practice).

In the event that there are interruptions during infusion, the total allowed time should not exceed 8 hours at room temperature. If either preparation time or infusion time exceeds the time limits a new dose must be prepared from new vials.

No incompatibilities between tremelimumab and polyvinylchloride or polyolefin have been observed. Tremelimumab solution should not be infused with other solutions or medications.

#### **8.2.12 Return and Retention of Study Drug**

All unused investigational products will be returned to a MedImmune-authorized depot or disposed of upon authorization by MedImmune according to the investigational site policy.

### **8.3 Combination of Durvalumab and Tremelimumab regimens**

Patients in the durvalumab + tremelimumab combination therapy phase will receive 1500 mg durvalumab via IV infusion q4w for up to 4 doses/cycles and 75 mg tremelimumab via IV infusion q4w for up to 4 doses/cycles, and then continue 750 mg durvalumab q2w starting on Week 16 for up to 8 months (18 doses) (see Figure 2). Fixed dosing is only for subjects with > 30kg body weight. Patients with a body weight ≤ to 30 kg will be excluded. If a patient becomes <30kg on study, please see additional dosing instructions per each agent

Tremelimumab will be administered first, followed by durvalumab. The duration for each will be approximately 1 hour (± 5 minutes). A 1-hour observation period is recommended after the first infusion of durvalumab and tremelimumab. If no clinically significant infusion reactions are observed during or after the first cycle, subsequent infusion observation periods can be at the Investigator's discretion (suggested 30 minutes after each durvalumab and tremelimumab infusion).

#### **8.3.1 Study drug preparation durvalumab and tremelimumab**

Based on average body WT of 75 kg, a fixed dose of 750 mg Q2W durvalumab (equivalent to 10 mg/kg Q2W), 1500 mg Q4W durvalumab (equivalent to 20 mg/kg Q4W) and 75 mg Q4W tremelimumab (equivalent to 1 mg/kg Q4W) is included in the current study.

#### **8.3.2 Monitoring of dose administration**

Patients will be monitored during and after the infusion with assessment of vital signs at the times specified in the Study Protocol.

In the event of a ≤Grade 2 infusion-related reaction, the infusion rate of study drug may be decreased by 50% or interrupted until resolution of the event (up to 4 hours) and re-initiated at 50% of the initial rate until completion of the infusion. For patients with a ≤Grade 2 infusion-related reaction, subsequent infusions may be administered at 50% of the initial rate. Acetaminophen and/or an antihistamine (eg, diphenhydramine) or equivalent medications per institutional standard may be administered at the discretion of the investigator. If the infusion-related reaction is ≥Grade 3 or higher in severity, study drug will be discontinued (even during durvalumab monotherapy).

As with any antibody, allergic reactions to dose administration are possible. Appropriate drugs and medical equipment to treat acute anaphylactic reactions must be immediately available, and study personnel must be trained to recognize and treat anaphylaxis. The study site must have immediate access to emergency resuscitation teams and equipment in addition to the ability to admit patients to an intensive care unit if necessary

#### **8.3.3 Side Effects when durvalumab and tremelimumab are given together (see current IB for full details)**

Below are safety data from 61 subjects with lung cancer who received durvalumab

in combination with tremelimumab. Related side effects reported in subjects receiving the combination were:

Very Frequent – Expected to occur in more than 25% of people (more than 25 out of 100 people): Fatigue (26.2%)

Frequent – Expected to occur in 10% to 25% of people (10 to 25 out of 100 people): Diarrhea (21.3%), High level of amylase (increased amylase in your blood may indicate poor function of your pancreas; 13.1%)

Not Frequent – Expected to occur in 5% to less than 10% of people (5 to less than 10 out of 100 people): High level of alanine aminotransferase (ALT is a substance that is found in the blood and when high can indicate damage to the liver; 9.8%), Itching (9.8%), Decreased appetite (8.2%), High level of aspartate aminotransferase (AST is a substance that is found in the blood and when high can indicate damage to the liver; 8.2%), Inflammation of large intestine (8.2%), Rash (8.2%), Low level of blood thyroid stimulating hormone decreased (this may indicate that your thyroid is releasing too much thyroid hormone; 6.6%), High level of lipase (lipase is a substance that is found in the blood and when high can indicate damage to the pancreas; 6.6%). Intestinal perforation has been seen to occur in more increased frequency and severity when durvalumab and tremelimumab are used in combination.

Related and serious side effects reported in at least 2 subjects receiving the durvalumab and tremelimumab combination were: Diarrhea (8.2%), Inflammation of the large intestine (6.6%), Inflammation of the lung (3.3%), High level of AST (3.3%), High level of ALT (3.3%), High level of amylase (3.3%)

Related and serious side effects reported in at least 2 subjects receiving the durvalumab and tremelimumab combination were:

## **9.0 CORRELATIVES/SPECIAL STUDIES**

**Please refer to laboratory manual for additional details**

### **9.1 Tissue sample collection guidelines**

A fresh tissue biopsy of the primary tumor or a metastatic site at baseline and after 2 cycles of treatment will be collected. Re-biopsy after cycle 2 must be of the original biopsy site. In case of complete response, a biopsy of the original site will be re-biopsied, if feasible (i.e. chest wall metastasis), or another metastatic site may be used. The tumor lesion planned for biopsy must not be used as index lesion for assessment of disease unless there are no other lesions suitable for biopsy or the lesion used for biopsy is  $\geq 2$  cm in its longest diameter.

Fresh tissue biopsies will be performed using an image-guided core needle at the aforementioned time points (pretreatment, after 2 cycles) according to institutional practice. If clinically practical, subjects will undergo 4 core biopsies at each scheduled biopsy time point, ideally at least 3 core biopsies. Skin punch biopsies are acceptable, however, at least 2 punch biopsies that are at least 8mm in shortest diameter are necessary. All tissue samples will be immediately frozen in liquid nitrogen and then stored at  $-80^{\circ}\text{C}$ , full details are provided in the lab manual. Collected tissues at baseline will undergo a touch prep to be sent to pathology for standard of care testing.

Tumor samples will be stored and may be used for additional correlative studies at a later date such as, but not limited to, immunohistochemistry, tumor mutation analysis and proteomic analysis.

#### **9.2 Blood sample Collection Guidelines**

Research blood samples will be collected at baseline and 2 months, and at end of study or time of discontinuation).

80 mL of whole blood should be collected per lab manual instructions. Please ensure that tubes are completely filled at time of collection.

#### **9.3 Sample Processing, Storage, and Shipment**

Refer to the lab manual for sample processing, storage, and shipment information.

#### **9.4 Assay Methodology**

See lab manual for details.

### **10.0 STATISTICAL CONSIDERATIONS**

#### **10.1 Study Design/Study Endpoints**

This will be a single-arm, open-label, pilot phase II study to assess the efficacy and safety of durvalumab in combination with tremelimumab in patients with stage IV breast cancer which is HER2 negative. Patients who have completed the week 16 CT or nuclear bone scan will be evaluable for response endpoints. (*Note: Bone scans will be done only if the patient has bone disease. PET-CT is acceptable in place of bone scan, if a bone scan is contra-indicated for a patient's disease. The same modality used at baseline should be used throughout.*)

The **primary endpoint** is ORR, defined as number (%) of patients with at least one visit response of partial response (PR) plus complete response (CR) in patients with metastatic HER2 negative breast cancer treated with durvalumab in combination with tremelimumab using the Response Evaluation Criteria in Solid Tumors (RECIST) Version 1.1 (23). Any patient who has completed two months of study therapy is evaluable for this end point.

**Secondary endpoints** include PFS and OS, where PFS is defined as the time from date of treatment initiation until date of documented disease progression or death (by any cause in the absence of progression), and OS is defined as the time from date of treatment initiation until death due to any cause. Clinical benefit rate (SD for  $\geq$  12 weeks + PR + CR) will be assessed. Any patient who has completed two months of study therapy is evaluable for this end point.

The safety endpoints will be the number, frequency, and severity of adverse events (as defined by the NCI Common Terminology Criteria for Adverse Events or CTCAE version 4.03) will be recorded. Any patient treated with minimum 1 dose of either study drug will be evaluable for toxicity.

The expansion cohort will follow a similar design but only include patients with metastatic TNBC. Responses will be captured by RECIST v1.1.

**Exploratory endpoints** include serum and tissue-based biomarkers including: circulating tumor DNA, immunohistochemical expression of PD-L1; TILs; changes in tissue and peripheral T cell receptor sequencing, mutational and neoantigen burden, and immune-related candidate gene signatures at baseline.

Based on the fact that significant responses have been recently documented after progression when patients are started on next line of chemotherapy; a third exploratory objective is being added in order to capture response and duration of response to next line therapy.

Objective: To determine the response rate (RR) and duration of response (DoR) of next line

therapy after progression on durvalumab/ tremelimumab study regimen, for those patients who are able to submit detailed follow up data about subsequent treatment and response.

#### **10.2**

#### **Sample Size and Accrual**

A total of 35 patients (as needed) with metastatic breast cancer which is HER2 negative will be enrolled into this study and receive durvalumab in combination with tremelimumab, in order to get 28 evaluable for response. 15 patients with ER-positive disease and 15 patients with ER-negative disease will be enrolled (i.e. 2 cohorts with 14 evaluable each). Patients who have completed the week 8 CT or nuclear bone scan will be evaluable for response endpoints. Bone scans will be done only if the patient has bone disease. PET-CT is acceptable in place of bone scan, if a bone scan is contra-indicated for a patient's disease. The same modality used at baseline should be used throughout.

Using a Simon's two-stage design, we assume the undesirable overall response rate (null hypothesis) to be approximately 10%, and the alternate hypothesis to be approximately 30% based on previously published and presented data. Eleven patients will be added in the first stage. If 2 or more respond, then an additional 16 patients will be added for a total of 27. If 6 or more respond, then the hypothesis that the response rate is at least 30% is supported. This design has a Type I error rate of 4% and 80% power, and has a 70% chance of stopping early for futility after the first stage if the true response rate is 10%. The design is based on the complete sample and is not stratified by estrogen receptor status. ORR will also be calculated separately by receptor status, but the study is not powered for analyses within these subgroups.

For the expansion cohort we expect the ORR based on RECIST v1.1 to exceed 30% given our preliminary data. Using a Bayesian design assuming a prior beta distribution with parameters 0.3 and 0.7, there is a posterior probability of 0.81 that the ORR exceeds 30% if 8 or more responses out of 20 evaluable patients are observed.

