## **STUDY SUMMARY**

**NU Study Number: NU 15B01**  
**Other Study Number: MedImmune # ESR-14-10694 (D4190C00030)**

Title	A Single Arm Phase II Study Evaluating the Efficacy and Safety of Durvalumab (MEDI4736) In Combination With Tremelimumab In Patients with Metastatic HER2 Negative Breast Cancer: TNBC expansion cohort
Short Title	Durvalumab and Tremelimumab in Metastatic Breast Cancer
Version	Amendment 12 dated 8.31.2020
Study Design	Phase II
Study Center	Northwestern University
Objectives	
Primary Objective:  To evaluate overall response rate (ORR) in patients with metastatic HER2 negative breast cancer treated with durvalumab in combination with tremelimumab.
 
Expansion Cohort Objective: To evaluate overall response rate (ORR) in patients with metastatic triple negative breast cancer treated with durvalumab in combination with tremelimumab.
 
Secondary Objectives:  To evaluate PFS and OS in patients with metastatic HER2 negative breast cancer treated with durvalumab in combination with tremelimumab.  To evaluate clinical benefit rate in this population.  To evaluate safety and tolerability.
 
Exploratory:  To evaluate if serum and tissue-based immune-related biomarkers are modulated by therapy and predict response. (see Section 2.3 for details)  To assess response rates to next line therapy after progression

Sample Size	A total of 30 patients (15 ER+, 15 ER-) with metastatic breast cancer which is HER2 negative will be enrolled into this study and receive durvalumab in combination with tremelimumab in order to get 28 evaluable (14 ER+, 14 ER-) for response. Expansion cohort based will enroll 20 additional patients with TNBC to determine the posterior Bayesian probability that the response rate exceeds 30%.

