**NU Study Number: NU 15B01**

**Other Study Number: MedImmune # ESR-14-10694 (D4190C00030)**

**3.0 PATIENT ELIGIBILITY**

The target population for this study is patients with stage IV (metastatic) HER2 negative breast cancer (both male and female patients are eligible). This will be a single-center trial conducted at Northwestern University. The expansion cohort will only include metastatic TNBC.

Eighteen patients will be added in the first stage. If 4 or more respond, then an additional 10 patients will be added for a total of 28. A total of 30 subjects (15 ER+, 15 ER) will be needed to obtain a total of 28 evaluable patients (14ER+ and 14ER-) for this trial. The expansion cohort will include 20 evaluable patients with TNBC. Approximately 5 potentially eligible patients are seen per month, and it is anticipated that at least 2 per month will be accrued. Potential patients may be referred to the Principal Investigator (PI) at Northwestern University, [name] at [contact].

Eligibility will be evaluated by the study team according to the following criteria. Eligibility waivers are not permitted. Subjects must meet all of the inclusion and none of the exclusion criteria to be registered to the study. Study treatment may not begin until a subject is registered. Please refer to Section 11 for complete instructions regarding registration procedures.

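### The general cohort has two different two-stage rules, and the only success cutoff belongs to 27 patients although 28 evaluable are planned

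*Combined protocol and SAP*

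**What the plan says.** **General cohort, Section 10.2.** Enrolment is given as "A total of 35 patients (as needed) with metastatic breast cancer which is HER2 negative will be enrolled", to reach 28 evaluable. The next sentence splits enrolment into 15 ER-positive and 15 ER-negative, with 14 evaluable in each. The Simon design follows, with a null response rate of about 10% and an alternative of about 30%. Its opening stage is given as "Eleven patients will be added in the first stage", and the rule for going on reads "If 2 or more respond, then an additional 16 patients will be added for a total of 27". Success is 6 or more responses. The section states a type I error of 4%, 80% power and a 70% chance of early stopping under the null.

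**General cohort, Section 3.0.** The first stage is 18 patients. At 4 or more responses, 10 more are added for a total of 28. No final success cutoff is given. Enrolment: "A total of 30 subjects (15 ER+, 15 ER) will be needed to obtain a total of 28 evaluable patients". The Study Summary agrees on 30 enrolled and 28 evaluable.

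**Interim result, Section 1.7.3.** Among the first 18 evaluable patients there were 3 responses.

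**Expansion cohort.** The Study Summary says "Expansion cohort based will enroll 20 additional patients with TNBC". Section 3.0 says "The expansion cohort will include 20 evaluable patients with TNBC", and the rule in 10.2 is 8 or more responses among 20 evaluable. Section 4.9 lets patients be added when needed for the response assessment.

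**The concern.** A two-stage design is defined by four integers: first-stage size, first-stage cutoff, total size and final cutoff. The current text gives one full set (11, 2, 27, 6) and one incomplete set (18, 4, 28, no final cutoff). The recruitment target used throughout matches the total of the incomplete set, while the stated error rates belong to the full one.

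Two decisions depend on this. The first is whether the cohort should have continued after stage one. The second is whether a given number of responses among 28 patients counts as success. On the second, the plan is silent about which cutoff applies once the 28th evaluable patient is included.

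**Working it through.** **Inputs.** From 10.2: p0 = 0.10, p1 = 0.30, n1 = 11, continue at c1 = 2, n = 27, success at c = 6. From 3.0: n1 = 18, c1 = 4, n = 28. Planned evaluable (Summary, 3.0, 10.2): 14 + 14 = 28.

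**Formulae.** With X1 ~ Bin(n1, p) and X2 ~ Bin(n − n1, p):

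- P(success) = Σ over x ≥ c1 of P(X1 = x) × P(X2 ≥ c − x). This is the type I error at p0 and the power at p1.
- P(early stop) = P(X1 ≤ c1 − 1).

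**Step 1: reproduce the 10.2 design (11, 2, 27, 6).**

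- Early stop at 10%: 0.3138 + 0.3835 = 0.697 (stated 70%).
- Type I error, terms for x = 2, 3, 4, 5 and x ≥ 6: 0.2131 × 0.0684 + 0.0710 × 0.2108 + 0.0158 × 0.4853 + 0.0025 × 0.8147 + 0.0003 = 0.0395 at full precision (stated 4%).
- Power, same terms at 30%: 0.1506 + 0.2313 + 0.2144 + 0.1316 + 0.0782 = 0.806 (stated 80%).

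The stated figures are therefore correct for 27 patients.

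**Step 2: apply the same formula at 28.**

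| First stage | Total | Success at | Type I error | Power |
|---|---|---|---|---|
| 11, 2 or more | 27 | 6 or more | 3.95% | 80.6% |
| 11, 2 or more | 28 | 6 or more | 4.50% | 82.2% |
| 11, 2 or more | 28 | 7 or more | 1.6% | 73.8% |
| 18, 4 or more | 28 | 6 or more (assumed) | 3.9% | 80.5% |
| 18, 4 or more | 28 | 7 or more (assumed) | 1.5% | 73.6% |

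The final cutoffs in the last two rows are assumptions, because 3.0 gives none.

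**Step 3: compare the first-stage rules.**

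| Rule | Stop if true rate is 10% | Stop if true rate is 30% |
|---|---|---|
| 10.2: fewer than 2 of 11 | 69.7% | 11.3% |
| 3.0: fewer than 4 of 18 | 90.2% | 16.5% |

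**Step 4: set the interim result against each rule.** Three responses in 18 is below 4, so the 3.0 rule is not met. The 10.2 rule needs the number of responses among the first 11 evaluable patients, which is not reported. The 3 responses could fall so that 0, 1, 2 or 3 are among those 11, so either outcome is possible.

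**Step 5: enrolment and the expansion cohort.** To reach 28 evaluable, 30 enrolled allows for 2/30 = 6.7% non-evaluable and 35 allows for 7/35 = 20%. For the expansion cohort, the Beta(0.3, 0.7) prior with 8 of 20 gives a Beta(8.3, 12.7) posterior and P(ORR > 30%) = 0.812. This matches the stated 0.81 and shows that the rule is written for 20 evaluable.

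**The case against.** The case for calling this editorial is fair in several parts.

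- **27 against 28.** With the cutoff left at 6, type I error stays below 5% and power rises. One more evaluable patient makes the receptor groups equal. This stands: the mismatch alone does little harm.
- **Section 3.0 may be leftover text.** Appendix E lists the 11-then-27 wording among the Amendment 8 changes. That is plausible, but both rules stand in the current version and neither section gives way to the other.
- **Timing.** General-cohort enrolment is finished and Appendix E records that the study closed in July 2020. This also stands, so the remedy bears on analysis and reporting and not on recruitment.

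Three stronger readings are tempting, and the documents do not support them.

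- **That 30 against 35 enrolled breaks the decision rules.** The 35 is qualified in a way that reads as a ceiling above 15 + 15. Section 10.3 labels the primary population ITT but defines it through evaluable patients. Only if every enrolled patient were counted with a cutoff of 6 would type I error rise to 5.7% (30 patients) or 9.0% (35 patients), and the plan does not say to do that.
- **That the expansion cohort will fall short of 20 evaluable and so lose its rule.** Sections 3.0 and 10.2 both count 20 evaluable, and 4.9 permits additions. No loss rate is given for that cohort. Nor would a fixed count of 8 necessarily carry over to a smaller cohort, since 7 of 16 already gives a posterior of 0.86.
- **That the trial ran through its futility stop.** The documents do not say which first-stage rule governed the interim look, and the count among the first 11 is missing.

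**Conclusion.** The point holds for the general cohort. The current text contains two incompatible first-stage rules, and its only success cutoff and error rates belong to 27 patients when 28 evaluable are planned.

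The 27-against-28 effect is small at a cutoff of 6: type I error rises by 0.55 percentage points (3.95% to 4.50%) and power by 1.6 points (80.6% to 82.2%). It would be larger if the cutoff were taken as 7, because power then falls to 73.8%, below the stated 80%. The first-stage conflict is the more serious part, since the reported 3 of 18 fails one rule and cannot be judged against the other.

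These figures assume exact binomial responses at 10% and 30%, and that evaluable patients are the denominator. The enrolment totals and the Summary's expansion figure are minor inconsistencies that change no decision rule.

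**What to change.** 1. Reconcile Sections 3.0 and 10.2 to the one two-stage design that was actually used, and say which rule governed the interim look and how many responses there were at that point. This should be settled from trial records and not by choosing a rule in the light of the results.
2. If the 10.2 design was used, either analyse the first 27 evaluable patients with success at 6 or more, or restate the rule for 28 with its own error rates (4.5% and 82% with success at 6 or more).
3. If the 3.0 first stage was used, add the missing final cutoff and its error rates. At 6 or more these are 3.9% and 80.5%.
4. As consistency edits, describe 35 as an enrolment ceiling over the planned 30, and change the Study Summary so that the expansion cohort is 20 evaluable, matching 3.0 and the 8-of-20 rule.

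The cost is wording only. The one visible consequence is that the stated type I error becomes 4.5% if 28 is kept with the 10.2 first stage and a cutoff of 6.
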